Study objectives:	
 1. Comparative assessment of efficacy of Primapur[®] (follitropin alfa), a solution for subcutaneous administration, and GONAL-F[®] (follitropin alfa). 2. Comparative assessment of safety of Primapur[®] (follitropin alfa), a solution for subcutaneous administration, and GONAL-F[®] (follitropin alfa).
Study design:	
multicenter randomized embryologically blinded parallel group comparative therapeutic equivalence study of Primapur[®], a solution for subcutaneous administration, and GONAL-f[®], a solution for subcutaneous administration.

Planned number of patients	
110 female patients randomized into two equal groups of 55 subjects receiving study referenced drugs.

Study centers	
3 specialized medical centers in the Russian Federation

Study population:	
Women aged 20-35 with established causes of infertility (tubal factor, male factor (oligoasthenoteratozoospermia) and indications for the use of assist reproductive technologies (ART).

Inclusion criteria:	
 1. Women with established causes of infertility and indications for the use of ART methods, according to the Order of the Ministry of Health of the Russian Federation "On the use of assisted reproductive technologies, contraindications and limitations to their use" No. 107 n dated August 30, 2012. 2. Causes of infertility: Tubal factor and/or male factor (oligoasthenoteratozoospermia). 3. Female patients aged 20 to ≤35 with an independent regular menstrual cycle (duration: 21 to 35 days); 4. First or second attempt of IVF/ICSI.

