
Exclusion criteria:
	
 1. The patient's refusal to participate in the study at any stage. 2. Development of one of the exclusion criteria. 3. Development of severe OHS. 4. Ineffective stimulation of FSH (no pool of growing follicles) on Day 5 or Day 8 of stimulation. 5. Necessity of cryopreservation of embryos due to cancellation/postponement of embryo transfer according to the indications. 6. Development of AEs/adverse reactions that cause an unacceptable risk to the patient's health if the patient continues to participate in the study

	
and requires the withdrawal of the therapy and/or the concomitant therapy.
 
7. The patient's major violation of the medical investigator's recommendations under the protocol and deviation from the study procedures.
 
8. Occurrence of concomitant somatic diseases/symptoms or aggravation of chronic diseases not associated with taking medications (at the discretion of the medical investigator), requiring changes in therapy and observation procedures that are incompatible with the clinical study protocol.

Dosage and duration of treatment; route of administration:
	
QD, starting from Day 2 of Day 3 of menstrual cycle, 150 IU of study/reference drug per day, according to the protocol controlled superovulation induction, with the use of GnRH antagonist, providing the ability to adjust the dose of study drug on Day 5 or Day 8 of stimulation as a result of transvaginal ultrasound of ovaries. The duration of stimulation is no more than 15 days.

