
Period of PI/PR therapy. Up to 15 days (2 weeks and 1 day).
	
Visit 2. Randomization. Day 1. Beginning of the stimulation protocol (2-3 day of the menstrual cycle)
 
 1. Selection criteria check. Decision of randomization into a clinical study or registration of a screening failure. 2. Carrying out randomization, using IWRS, distribution into groups: group FSG031 of Primap[®], a study drug, or group FSG032 of GONAL-f[®], a reference drug. 3. Inspection: 
 ✓ Registration of patient complaints. ✓ Registration of changes in concurrent conditions and concomitant therapy. ✓ Physical examination ✓ Measurement of vital parameters, particularly HR, BP, RR, body temperature. ✓ Prescription of the stimulation protocol. 4. Introduction of the 1st dose of PI/PR. 5. Registration of adverse events/reactions after the first dose of PI/PR. 
Visit 3. Day 5-8 of stimulation.
 
The 3rd visit procedures are aimed at a primary evaluation of the therapy efficacy. The patient may be invited to conduct the procedure once (on the 5th day) or several times (additionally on the 6th, 7th, 8th days of the therapy) at the investigator's discretion, depending on the results of the required diagnostic procedures. 3 visit procedures:
 
 1. Instrumental examinations: 
 ✓ Transvaginal ultrasound of ovaries. Follicle count and determination of follicle diameter in both ovaries. 2. Inspection: 
 ✓ PI/PR dose adjustment (in the absence of follicles more than 10 mm on 5-8 days of stimulation).

- ✓ Registration of patient complaints, concurrent conditions and concomitant therapy.
 - ✓ Physical examination
 - ✓ Measurement of vital parameters, particularly HR, BP, RR, body temperature.
3. *Exclusion of the patient from the study in case of failed stimulation (with no response to FSH administration on day 5-8 of stimulation).*
 4. Initiation of GnRH antagonist administration (when the lead follicle is about 14 mm);
 5. Registration of adverse events/reactions.

Additional visit for GnRH antagonist administration (if required).

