
Follow-up period. 10 weeks.
	
Visit 5. Puncture of follicles. IVF/ICSI. No more than 37 hours from the introduction of the ovulation inducer (Visit 4).
 
 1. Examination before follicle puncture: 
 ✓ Registration of patient complaints. ✓ Registration of changes in concurrent conditions and concomitant therapy. ✓ Physical examination ✓ Measurement of vital parameters. 2. Blinding of the studied therapy at the stage of oocyte counting performed by the embryologist (by coding the data on the study drugs in the patient's electronic medical record viewed by the embryologist). 3. Puncture of follicles: 
 ✓ Ultrasound. Follicle count before anesthesia and follicle puncture. ✓ USG-guided puncture of follicles under general anesthesia. ✓ Obtained oocyte counting performed by the embryologist. 4. Carryinh out of IVF/ICSI. 
 ✓ Determination of the number of mature/immature oocytes. 5. Registration of adverse events/reactions. 6. Exclusion of the patient from the study if cryopreservation of embryos is required according to the indications. 
Visits 6 and 7: Transfer of the embryo(s)/blastocyst(s) into the uterine cavity. Up to 5 days after Visit 5.
 
 1. Inspection: 
 ✓ Registration of patient complaints. ✓ Registration of changes in concurrent conditions and concomitant therapy. ✓ Physical examination ✓ Measurement of vital parameters, particularly HR, BP, RR, body temperature. 2. USG-guided transfer of embryos/blastocysts (1 or 2, but not more than 2). 3. Registration of adverse events. 4. Exclusion of the patient from the study if cryopreservation of embryos is required according to the indications.

Telephone contact. Day 7 from embryo/blastocyst transfer.

1. Registration of patient complaints, changes in concurrent conditions and concomitant therapy. State assessment.
2. Registration of adverse events.

Visit 8: Confirmation of biochemical pregnancy/early study termination. Day 12-17 from embryo/blastocyst transfer.

1. Laboratory testing:
 - ✓ hCG blood test.
2. Inspection:
 - ✓ Registration of patient complaints.
 - ✓ Registration of changes in concurrent conditions and concomitant therapy.
 - ✓ Physical examination
 - ✓ Measurement of vital parameters.
3. Registration of adverse events.

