Unscheduled visit.	
At any stage of the study, an additional visit to the center can be made at the investigator's discretion if a patient has a complaint requiring a reproductologist's intervention for the purpose of individually monitoring the superovulation induction course and monitoring the pregnancy course in order to reduce the risk of developing any adverse reaction and to monitor the therapy efficacy.
 
Additional visits may include, but not be limited to, the following procedures (depending on the indications):
 
 1. Instrumental examinations: 
 ✓ Transvaginal ultrasound of ovaries. 2. FSH dose adjustment. 3. Physical examination. 4. Measurement of vital parameters. 5. Registration of patient complaints. 6. Complete blood count. 7. Biochemical blood test. 8. Coagulogram. 9. General urine analysis.

	10. Blood test for hormones and other clinically relevant markers.

*The presence of anti-FSH antibodies will be determined centrally at the laboratory of Exacte Labs LLC and/or an additional research laboratory on a contractual basis (if required). The study results will be attached to the initial documentation of the investigation site. Immunogenicity will be evaluated using the following methods: enzyme immunoassay and surface plasmon resonance for positive samples.
	

Efficacy evaluation criteria:
	
Study endpoints per patient:
 
Primary point:
 
 • Total number of aspirated oocytes. 
Secondary points:
 
 • Number of follicles \geq 16 mm on the day of administration of hCG. • Number of mature oocytes (MII stage). • Number of fertilized oocytes. • Number of patients with embryo transfer (days 2-3). • Number of patients with blastocyst transfer (days 4-5). • Total dose of a human rFSH product injected (IU). • Number of days of stimulation. • Percentage of patients who needed a FSH dose adjustment on the 5th-8th day of stimulation. • Number of patients who abandoned the IVF/ICSI program in the process of stimulation. • Number of non-responders to stimulation. • Incidence of biochemical pregnancies. • Incidence of clinical pregnancies (up to 10 weeks after the embryo(s) transfer).

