
Statistical processing of data:
	
Description of methods of statistical data processing
 
The quantitative data obtained during the study will be tested for normal distribution, using the Shapiro-Wilk test and, if necessary, the F-test of equality of variances. For variables corresponding to the normal distribution, mean values and standard deviation of the mean will be calculated; Quantitative data not corresponding to the normal distribution will be described using the median and interquartile interval. Qualitative variables will be described using absolute and relative frequencies (percentages).
 
In order to compare two groups of normally distributed quantitative data, the Student's t-test will be used; if quantitative data distribution differs from normal values, the Mann-Whitney U test will be used. For intergroup comparisons by qualitative characteristics, the Fisher's exact test will be used; correction of p-value in the case of multiple hypotheses will be realized through the Bonferroni adjustment.
 
Applicable significance level
 
In this study, the indicators are considered statistically significant at the bilateral p-value level <0.05.
 
Therapeutic equivalence criteria.
 
The conclusion about the therapeutic equivalence of the two drugs will be made if the difference between the mean values of the total number of oocytes obtained when applying both drugs lies within the limits of the equivalence threshold (± 3.4 oocytes).
 
Procedures for accounting of missing, not-analyzable and uncertain data.
 
CRF information will be entered into the computer database, and data will be electronically and visually verified for completeness, and allowable ranges will be checked. All errors detected during the quality control process will be corrected. In the presence of deviating data ("outliers"), the correctness of their measurement and introduction into the database will be rechecked. Data will be analyzed twice: with and without "outliers". If the results are stable to the "outliers", a calculation that includes all available values of the variable will be used. If there is the influence of "outliers" on the initial result, the results obtained both taking into account the deviating data and without deviating data will be presented and commented on.

Calculation of sample size

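### Patients withdrawn for failed stimulation have no analysis set and no oocyte value, so the primary mean will in practice cover only those who reach retrieval

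*Combined protocol and SAP*

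**What the plan says.** The primary endpoint, under Efficacy evaluation criteria, is "Total number of aspirated oocytes", and the endpoints are defined per patient. Under Therapeutic equivalence criteria, the conclusion is drawn "if the difference between the mean values of the total number of oocytes obtained when applying both drugs lies within the limits" of ±3.4 oocytes. No population is named there.

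Randomisation and the first dose take place at Visit 2. The Visit 3 procedures then include: "Exclusion of the patient from the study in case of failed stimulation (with no response to FSH administration on day 5-8 of stimulation". The second list headed Exclusion criteria, which governs withdrawal, gives the same ground as "Ineffective stimulation of FSH (no pool of growing follicles) on Day 5 or Day 8 of stimulation". Oocytes are first counted at Visit 5.

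The section "Procedures for accounting of missing, not-analyzable and uncertain data" deals with data entry, range checks and outliers. It sets no value for a patient without a count.

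Blinding is described only for the embryologist: the design is a "multicenter randomized embryologically blinded parallel group comparative therapeutic equivalence study", and Visit 5 specifies "Blinding of the studied therapy at the stage of oocyte counting performed by the embryologist". None is described for the investigator who decides that stimulation has failed.

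A later withdrawal ground is different in kind: "Exclusion of the patient from the study if cryopreservation of embryos is required according to the indications". Those patients have already had their oocytes counted.

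**The concern.** Failed stimulation is the most extreme lack of effect an FSH product can show. A patient withdrawn for it has been randomised and dosed, but has no retrieval and so no recorded count. With no analysis set and no rule for her value, the natural result of following the plan is a mean over patients with retrieval. That population is selected after randomisation by response to the drug, so randomisation no longer protects the comparison.

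Two analysts could also follow the text and differ: one reads a stopped cycle as zero aspirated oocytes per patient, the other as no observation. Other withdrawals before retrieval (refusal, adverse event, severe OHS, major violation, intercurrent illness) leave the same gap.

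At stake is whether the ±3.4 conclusion describes all women given the drug or only those who responded. Non-responders and abandoned cycles are secondary counts, so an imbalance could be seen, but the equivalence criterion does not use them.

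**Working it through.** **Inputs from the documents.** 55 per arm; SD 6; margin d = 3.4; alpha 0.05; power at least 80%; assumed means 12.0 (test) and 10.9 (reference). No non-response rate is given, so the numbers of exclusions, k, below are assumptions.

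**1. The plan's own figure.** The sample-size formula (noncentral t, true difference 0, one-sided 0.05 for each of the two tests) gives power 0.809 at 55 per arm and 0.7997 at 54. The stated 55 reproduces.

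**2. Shift in an arm mean from exclusions.** If k of 55 patients, each of whom would have yielded v oocytes, are dropped from an arm whose full mean is m:

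shift = (55m − kv)/(55 − k) − m

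With m = 10.9 and v = 0:
- k = 1: 599.5/54 − 10.9 = 0.20 (6% of 3.4)
- k = 3: 599.5/52 − 10.9 = 0.63 (18%)
- k = 5: 599.5/50 − 10.9 = 1.09 (32%)

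With v = 3 the shifts are 0.15, 0.46 and 0.79. With m = 12.0 and v = 0 they are 0.22, 0.69 and 1.20.

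**3. Direction.** Suppose 3 exclusions, all in the test arm, reference mean 10.9 and SD 6. The 90% interval used here corresponds to the two one-sided tests in the sample-size section; the equivalence criterion itself names no interval.

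- *Test lower by 1.0 among retrieved patients.* Retrieved only (52 v 55): −1.0 ± 1.93, that is −2.93 to 0.93, inside the margin. With zeros, the difference is 9.9 × 52/55 − 10.9 = −1.54; the test-arm variance is (52/55) × 36 + (3/55)(52/55) × 9.9² = 39.09; the pooled SD is 6.13 and the half-width 1.94. The interval is −3.48 to 0.40, just outside.
- *Test higher by 1.5 among retrieved patients.* Retrieved only: upper limit 1.5 + 1.93 = 3.43, outside. With zeros, the difference is 12.4 × 52/55 − 10.9 = 0.82 and the upper limit 2.80, inside.

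With 3 test-arm exclusions, retrieved-only passes while zeros fails for retrieved differences of about −1.47 to −0.92. The reverse holds for about +1.47 to +2.12. At −1.0, one exclusion (−3.09 to 0.73) or two (−3.29 to 0.57) do not change the result. If the point difference alone is compared with ±3.4, as the criterion is worded, all four analyses above pass.

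**4. Power if stopped cycles count as 0.** With p = k/55 in both arms and SD 6 among the others:

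SD = √[(1 − p) × 36 + p(1 − p) × m²]

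| Zeros per arm | SD (m = 10.9) | Power at 55, zeros | Power if dropped | n per arm for 0.80, zeros |
|---|---|---|---|---|
| 1 | 6.12 | 0.79 | 0.80 | 57 |
| 3 | 6.34 | 0.75 | 0.78 | 61 |
| 5 | 6.52 | 0.72 | 0.76 | 64 |

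With m = 12.0 the zeros analysis has power 0.78, 0.73 and 0.69 and needs 57, 63 and 67 per arm.

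**The case against.** A reader might infer that the gap favours the sponsor's conclusion. The documents do not support that. They give no failure rate and no direction, and the sample-size section assumes the test product yields more oocytes (12.0 v 10.9). In that situation, excess failures in the test arm make zeros pull the difference towards equivalence, as the second case in the working shows. For the same reason, replacing the retrieved-only mean with zeros alone would not be reliably conservative.

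A reader might also infer that the plan prescribes a responders-only analysis. It does not; it leaves the population open. The per-patient wording even permits reading a stopped cycle as zero, but the equivalence criterion does not say so.

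The remaining objections bear on size, and they stand:
- Eligibility (AMH at least 1.0 ng/mL, AFC 4 to 15, no earlier poor response) should keep failures few. Dose adjustment when no follicle exceeds 10 mm on days 5-8 should reduce them further.
- With identical responders and zeros for failures, a gap in failure rates of about 28 to 31 percentage points (3.4/12.0 to 3.4/10.9) is needed before the all-treated difference reaches the margin.
- The change of conclusion in the working needs an interval that the criterion does not state, three exclusions in one arm and a narrow range of differences. It shows what is possible, not what is likely.
- The power loss assumes SD 6 describes patients without zeros. If the cited studies' counts already include zeros, the loss is overstated.

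None of this supplies the missing analysis set or the missing value.

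**Conclusion.** The concern holds. Randomised, dosed patients are withdrawn for an efficacy failure before the primary endpoint is counted, and the plan neither places them in an analysis set nor gives them a value. The primary comparison is therefore likely to be conditioned on response and can conceal an imbalance in non-response. It can bias the difference in either direction, depending on which arm has more failures and which has the higher yield.

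The likely effect is modest: about 0.6 oocytes for a net excess of 3 zero-yield exclusions in 55 at a mean of 10.9. That figure rests on assumed exclusions, since the documents give no rate. The rule should be settled before the data are compared by arm; the material does not show that the conclusion would be wrong without it.

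**What to change.** In the statistics section, under Therapeutic equivalence criteria and the missing-data procedures:

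1. Define the all-treated analysis: every randomised patient who received study drug, analysed as randomised, on aspirated oocytes per patient. Use 0 for any cycle stopped before retrieval for non-response. Keep the observed count for anyone withdrawn after retrieval, including for cryopreservation.
2. Analyse patients with retrieval only as well, and conclude equivalence only if both analyses meet the ±3.4 criterion. This covers bias in either direction.
3. For other withdrawals before retrieval, state how the missing count is handled, with 0 as a sensitivity analysis only. Zero is a poor main rule for severe OHS in particular, because it records an over-response as no response.
4. Restate the power.

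**Cost.** No new type of data is needed, since non-responders and abandoned cycles are already secondary counts. Power in the all-treated analysis falls from 0.81 to about 0.79, 0.75 or 0.72 with 1, 3 or 5 zeros per arm (true difference 0, SD 6 among responders, mean 10.9), and the joint requirement can have no higher power than that. Restoring 0.80 in the all-treated analysis alone would take 57, 61 or 64 per arm. The 27% allowance is worded for screened patients (140 screened, 110 randomised), so as worded it leaves no reserve after randomisation. Dropping these patients also costs power (0.80, 0.78 or 0.76).

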For the present study, calculation of sample size is based on data on the number of oocytes obtained from clinical studies of GONAL-F® (follitropin alfa) and its biosimilars (*Rettenbacher M. et al. Reprod Biomed Online. 2015;30(5):504-13; Strowitzki T. et al. Reprod Biol Endocrinol. 2016;14:1.; Moon SY et al. J Obstet Gynaecol Res. 2007;33(3):305-15*).

Based on the results of these studies, it is assumed that the total number of oocytes obtained for study and reference product of follitropin alfa is 12.0 ± 5.9 and 10.9 ± 6.5 , respectively.

To suppress the release of endogenous LH, ART programs use either GnRH antagonist or GnRH agonist, together with the use of follitropin. According to meta-analyzes (*van Wely M. et al. Cochrane Database Syst Rev. 2011;(2):CD005354; Al-Inany HG et al. Cochrane Database Syst Rev. 2016; 4: CD001750*), the use of GnRH agonists and antagonists in ART programs leads to the same number of live births; and the use of GnRH antagonist statistically significantly reduces the risk of serious adverse events, compared with the use of GnRH agonist; however, the number of oocytes obtained may differ slightly in the protocols with the use of GnRH antagonists, which is explained by the difference in growth of a size-synchronized pool of follicles.

In accordance with this, the following hypotheses have been formulated:

H0 (zero hypothesis): $\mu_A - \mu_B \leq -d, \mu_A - \mu_B \geq +d$

H1 (alternative hypothesis): $-d < \mu_A - \mu_B < +d$

where μ_A and μ_B are the selective average number of oocytes of study drug and reference drug (GONAL-F®).

The required number of patients in equal parallel groups was calculated according to the following formula (*Julious, SA. Statist. Med. 2004; 23:1921-1986*):

$$1 - \beta = \text{Probt}(-t_{1-\alpha, n_A(r+1)-2, n_A(r+1)-2, \tau_2}) - \text{Probt}(t_{1-\alpha, n_A(r+1)-2, n_A(r+1)-2, \tau_1})$$

where τ_1 and τ_2 are the uncertainty parameters calculated by the following formulas:

$$\tau_1 = \frac{((\mu_A - \mu_B) + d)\sqrt{rn_A}}{\sqrt{(r+1)\sigma^2}} \quad \tau_2 = \frac{((\mu_A - \mu_B) - d)\sqrt{rn_A}}{\sqrt{(r+1)\sigma^2}}$$

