Thus, to provide a study power of at least 80% at a significance level $\alpha=0.05$, a standard deviation of the number of oocytes obtained equal to $\sigma=6$ and an equivalence threshold value $d = 3.4$ oocytes, the required sample size is 55 subjects per each group (n_A) and only 110 subjects in total; taking into account 27% drop out, the number of screened patients is recommended to be increased to 140.

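### Equivalence is judged on the observed mean difference alone, so the written rule passes a product that differs by the full margin half the time instead of 5% of the time

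*Combined protocol and SAP*

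**What the plan says.** All the relevant text is in the study summary, under Statistical processing of data.

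- **Therapeutic equivalence criteria.** Equivalence is concluded on one condition: "difference between the mean values of the total number of oocytes obtained when applying both drugs lies within the limits of the equivalence threshold", with that threshold at ±3.4 oocytes. No interval, confidence level or one-sided test is attached.
- **Description of methods.** Two groups are compared by Student's t-test, or by Mann-Whitney if the data are not normal. Neither test is linked to the equivalence conclusion.
- **Applicable significance level.** The general statement is that "the indicators are considered statistically significant at the bilateral p-value level <0.05".
- **Calculation of sample size.** The null hypothesis is non-equivalence (difference at or beyond ±d) and the alternative is a difference strictly inside ±d. The two means in these hypotheses "are the selective average number of oocytes of study drug and reference drug". Power comes from a non-central t formula with a critical value at 1-alpha on each side. The calculation is meant "to provide a study power of at least 80% at a significance level" of 0.05, with SD 6 and d = 3.4, and arrives at 55 per group.

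**The concern.** The decision rule and the sample size describe two different procedures. The hypotheses and power formula belong to two one-sided tests (TOST), in which the estimate must lie inside the margin by enough to rule out a true difference of 3.4. The criterion asks only that the estimate itself be inside. The tests that are named cannot fill the gap: a t-test or Mann-Whitney test at two-sided 0.05 tests a null of no difference, and a non-significant result does not reject non-equivalence.

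The level is also unsettled. The general rule is two-sided 0.05, whereas the sizing formula spends 0.05 on each side, which corresponds to a 90% interval. Anyone adding an interval later would have to choose between 90% and 95%, possibly after seeing the data.

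This is the sole criterion on the primary endpoint of a Phase III equivalence study whose declared final goal is marketing authorization. Followed as written, it could declare the products equivalent while the plan's own t-test shows a significant difference between them.

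**Working it through.** **Inputs.** n = 55 per group, SD = 6, d = 3.4, alpha = 0.05, power at least 80% (all from Calculation of sample size). The calculation does not state the true difference used with SD 6; 0 is tried first.

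**1. Reproduce the plan's sample size.** With equal groups, df = 2n - 2 and SE = SD × sqrt(2/n):

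power = Probt(-t(1-alpha, df); df, tau2) - Probt(t(1-alpha, df); df, tau1), where tau1 = (difference + d)/SE and tau2 = (difference - d)/SE.

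| Level per side | True difference | Power at 55 per group | n per group for 80% |
|---|---|---|---|
| 0.05 | 0 | 80.9% | 55 |
| 0.025 | 0 | 67.5% | 67 |
| 0.05 | 1.1 | 62.6% | 85 |

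At 54 per group the first row gives 79.97%, so 55 is the smallest size reaching 80%. Of these three variants, only 5% per side with zero difference returns 55. The trial was sized for TOST at 5% per side, that is, a 90% interval inside ±3.4.

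**2. Error rate of the written rule.** SE = 6 × sqrt(2/55) = 1.144. Under a normal approximation for the observed difference, the rule passes with probability

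Phi((3.4 - D)/1.144) - Phi((-3.4 - D)/1.144), where D is the true difference.

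- D = 3.4: Phi(0) = 0.50; the second term is negligible.
- D = 4.0: Phi(-0.524) = 0.30.
- D = 4.5: Phi(-0.961) = 0.17.
- D = 0: 2 × Phi(2.97) - 1 = 0.997.

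The formula in step 1 gives the TOST pass rate at the same values:

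| True difference | Written rule | TOST, 5% per side |
|---|---|---|
| 0 | 99.7% | 80.9% |
| 3.4 | 50% | 5.0% |
| 4.0 | 30% | 1.5% |
| 4.5 | 17% | 0.5% |

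A simulation of 400,000 trials at D = 3.4 gave 50.1% for the written rule, 5.0% for a 90% interval and 2.5% for a 95% interval. The 50% does not depend on the SD or sample size: it was unchanged for SD 5.9 to 6.5 and 40 to 70 per group, because an estimate centred on the margin falls inside it half the time.

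**3. What observed difference passes.** The 90% half-width is t(0.95, 108) × SE = 1.659 × 1.144 = 1.90, so TOST needs an observed difference within about 3.4 - 1.90 = 1.50. For a 95% interval it is 1.982 × 1.144 = 2.27, leaving 3.4 - 2.27 = 1.13. The written rule accepts anything up to 3.4.

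**4. Conflict with the plan's own t-test.** At SD 6 the two-sided t-test is significant once the observed difference exceeds 2.27, so an observed difference between 2.27 and 3.4 counts as both significantly different and equivalent. At D = 3.4, 50.1% of simulated trials met the written rule and 16.2% met it without a significant t-test. The remaining 50.1 - 16.2 = 33.9%, about 34%, would declare equivalence alongside p < 0.05.

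**The case against.** The strongest reply is that TOST is already in the plan. The sample size section has the right null hypothesis, the right alternative, an alpha and a matching formula. The text is a summary with loose statistical wording; it even describes the means in its hypotheses as those that "are the selective average number of oocytes of study drug and reference drug", which blurs parameters and sample means. On that reading the criterion merely restates the alternative hypothesis, to be tested as the sizing implies, and the 50% applies only if the sentence is taken literally.

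It stands that a TOST or interval analysis may well have been intended, and that the 50% belongs to the sentence as written. But the hypotheses serve the sample size and nothing carries them into the analysis. An analyst who followed the criterion under its own heading would compute no interval. Requiring a non-significant t-test as well, which the plan does not do, would still leave about 16% false equivalence at the margin.

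Two further points are fair but separate. The sample size section assumes means of 12.0 and 10.9, a difference of 1.1, at which TOST power with 55 per group is 62.6%. And the switch to Mann-Whitney after a normality test could reach the primary endpoint. Neither rescues the written rule.

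**Conclusion.** The concern holds. As written, the primary conclusion rests on a point estimate, with a false-equivalence rate at the margin of 50% against the 5% per side for which the trial was sized. The rates at 4.0 and 4.5 oocytes (30% and 17%, against 1.5% and 0.5%) assume 55 analysed per group, SD 6 and an approximately normal difference in means. The 50% needs only an unbiased, symmetric estimate and a negligible chance of falling beyond the opposite margin. The 5% comparator rests on reading alpha as per one-sided test, which the exact reproduction of 55 supports; under a 95% interval it would be 2.5%. This must be corrected before the result is used to claim equivalence.

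**What to change.** Replace the criterion with a sentence such as:

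> Therapeutic equivalence is concluded if the two-sided 90% confidence interval for the difference in mean number of aspirated oocytes (two one-sided t-tests, each at 5%) lies entirely within -3.4 to +3.4.

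State that the two-sided 0.05 level applies only to the secondary comparisons. It is also worth saying that the interval for the primary endpoint is computed on means whatever the normality test shows, so that the Mann-Whitney switch cannot displace it.

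The cost is a small edit to the statistical section, with no new patients, data or margin. The criterion becomes stricter, but it is the one the sizing formula already assumes. If a 95% interval is required instead, power at 55 per group and zero difference must be restated as 67.5%; keeping at least 80% would take 67 per group.

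### When the analyses with and without outliers disagree, the plan names neither as deciding equivalence, and it does not define an outlier

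*Combined protocol and SAP*

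**What the plan says.** All the relevant text is in the Combined protocol and SAP, under *Statistical processing of data*.

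- *Procedures for accounting of missing, not-analyzable and uncertain data*: errors found in quality control are corrected. If deviating values are present, their measurement and entry are rechecked. Then "Data will be analyzed twice: with and without" them.
- Same section, results stable: the calculation on all available values is used.
- Same section, results not stable: the results with and "without deviating data will be presented and commented on". Nothing says which of the two carries the conclusion.
- *Therapeutic equivalence criteria*: equivalence is concluded if the difference in mean oocyte number "lies within the limits of the equivalence threshold", ±3.4 oocytes. No data set is named.
- No section gives a numerical rule for calling a value deviating.

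**The concern.** The plan has a governing analysis only when the choice of analysis makes no difference. When the two runs disagree, the plan can be followed to the letter and still give no answer on equivalence.

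The values in question are mostly real. Errors are corrected and flagged values rechecked before the second run, so what that run drops is mainly verified oocyte counts. With planned values of 12.0 ± 5.9 and 10.9 ± 6.5, a count cannot fall 2 SD below its mean (12.0 − 11.8 = 0.2 and 10.9 − 13.0 = −2.1, against a floor of zero, so only a zero count in the first arm could qualify). Extremes will therefore be almost entirely high responses.

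The direction matters as well. In an interval-based equivalence test, dropping tail values reduces the SD, which makes equivalence easier to show. With no cut-off fixed, the definition of an outlier could also be settled after the results are seen. At stake is the single conclusion on which the trial's biosimilarity goal depends.

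**Working it through.** **1. The plan's own figure.** Inputs from *Calculation of sample size*: SD σ = 6, margin d = 3.4, α = 0.05, power at least 80%, equal arms. The plan's noncentral-t formula with a true difference of 0 and n = 55 gives:

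- noncentrality = d√n / √(2σ²) = 3.4 × 7.416 / 8.485 = 2.97
- critical t (108 df, 0.05 per side) = 1.659
- power = 80.9%

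So 55 per arm reproduces. (The normal approximation 2σ²(1.645 + 1.282)²/d² gives about 53.3.) At 0.025 per side the formula needs 67 per arm. The design therefore rests on two one-sided tests (TOST) at 5% each, and the sample size is not in question here.

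**2. Why trimming helps.** With SD 6 the standard error is 6 × √(2/55) = 1.144. TOST passes only if the absolute observed difference is below 3.4 − 1.659 × 1.144 = 1.50. If trimming lowers the SD to 5.4 (about what the 1.5×IQR rule does to negative binomial counts), the limit becomes 3.4 − 1.659 × 5.4 × 0.1907 = 1.69, ignoring the few patients lost.

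**3. Size.** Simulation of 100,000 trials: 55 per arm, SD 6 in both arms, true difference exactly 3.4, TOST at 5% per side, outliers removed within arm. The distributions and cut-offs are assumptions, so a range is shown. Entries are false-equivalence rates.

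| Distribution | Cut-off | All values | Trimmed only | Either passes | Both must pass |
|---|---|---|---|---|---|
| Negative binomial | 1.5×IQR | 5.0% | 7.0% | 8.0% | 4.0% |
| Negative binomial | 3 SD | 5.0% | 5.7% | 6.3% | 4.4% |
| Negative binomial | 2 SD | 5.0% | 6.7% | 7.7% | 4.1% |
| Normal | 1.5×IQR | 5.1% | 6.5% | 7.1% | 4.5% |
| Normal | 3 SD | 5.1% | 5.4% | 5.6% | 4.9% |
| Normal | 2 SD | 5.1% | 8.7% | 9.5% | 4.3% |

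A separate run of 20,000 trials with negative binomial counts and a 3×IQR cut-off gave 5.1% for either passing, which is no material inflation. With the plan's quoted SDs of 5.9 and 6.5, that run gave 7.2% at 1.5×IQR and 4.9% at 3×IQR.

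**4. Sidedness.** *Applicable significance level* says "the indicators are considered statistically significant at the bilateral p-value level <0.05". If this were read as 0.025 per one-sided test, the all-values rate of 2.5-2.6% would become 2.9-5.7% when either passes.

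**5. How often the gap would matter.** At 5% per side the two analyses reach different conclusions in 0.7-5.2% of trials when the true difference is 3.4, and in 1.8-12% when it is 0.

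**The case against.** The strongest reply is that the text already comes close to a main analysis with a disclosed sensitivity check. The second run is triggered only by deviating values, these are rechecked first, the all-values calculation is the default, and both results are reported when they differ. This stands as far as it goes. A reader might infer that every analysis is duplicated, or that real counts disappear from the report; the text supports neither.

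Second, a reader might infer that the plan grants two attempts at equivalence. It does not say so. Its silence also allows all values to decide, or both analyses to be required, and the last of these lowers the error rate. The inflation therefore belongs to one permitted reading.

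Third, a reader might construct much larger inflation by giving the higher-mean arm a much larger SD, or by adding a group of very high responders to one arm. The documents do not support those inputs. The quoted SDs run the other way (5.9 with the higher mean, 6.5 with the lower) and the planned SD is 6. Eligibility caps the antral follicle count at 15 and excludes polycystic ovarian syndrome and a history of 25 or more oocytes retrieved. Patients on a first attempt have no such history, so high responses remain possible, but nothing in the documents points to a tail concentrated in one arm.

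Fourth, the equivalence criterion as worded compares only the difference in means with ±3.4 and mentions no interval. Read literally, a smaller SD would not matter. That is a separate weakness. It does not close this gap, because dropping values can move the difference itself.

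What the reply does not supply is the missing rule. Presenting two conflicting results is transparent, but a yes-or-no equivalence conclusion still needs one deciding analysis.

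**Conclusion.** The point holds as a missing decision rule and a missing outlier definition. When the analyses disagree, the equivalence conclusion is undetermined and could rest on a post hoc removal of genuine oocyte counts.

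The size is modest and conditional. If either analysis could support the claim, false equivalence at the margin goes from about 5% to about 5-8% with negative binomial counts, and up to 9.5% with normal data and a 2 SD cut-off. If both had to pass, it would be about 4-5%. These figures assume TOST at 5% per side, 55 per arm, SD near 6, a true difference of 3.4, and cut-offs that the plan does not state.

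**What to change.** Replace the outlier rule with three statements:

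1. The primary analysis includes all observed oocyte counts; only documented data errors are corrected.
2. The equivalence conclusion rests on this analysis alone.
3. An analysis without values beyond a numerical cut-off, fixed before results are seen, is a sensitivity analysis and cannot change the conclusion.

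Under *Therapeutic equivalence criteria*, say that the ±3.4 comparison applies to that primary analysis.

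The cost is SAP wording only: no further patients or data, and the planned 55 per arm does not depend on trimming. The downside is a slightly wider interval if genuine extreme values occur.
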